1.2 Study design

This protocol presents a generic approach for conducting vaccine effectiveness studies using the indirect cohort method (also called case only or Broome method) in the elderly. This method was first proposed by Broome et al¹⁷ in early '80s to measure the effectiveness of PPSV vaccines. The design compares the vaccination coverage in IPD/ SpCAP cases due to vaccine serotypes to that of IPD/ SpCAP cases due to non-vaccine serotypes. Therefore, this design may be conducted only with data collected through the IPD/ SpCAP surveillance systems and provides a reliable estimate of vaccine effectiveness. However, this design is not appropriate to measure the VE against all type IPD/SpCAP or all cause CAP, and different designs need to be foreseen to answer questions related to these outcomes.

The design is based on the assumption that the vaccination coverage among the IPD cases due to non-vaccine serotypes is similar to the vaccination coverage in the source population giving rise to the IPD cases due to vaccine serotypes. This may be challenged if the vaccination is associated with a higher or a lower risk of getting non-vaccine serotypes. Two studies in the US¹⁸ and UK¹⁹, evaluated the potential bias introduced by the violation of this assumption when measuring the PCV7 vaccine effectiveness using data from US CDC ABCs and UK IPD surveillance systems in children. The results suggested that the bias that has been attributed to the violation of this assumption is low in the context of observational studies.

Other designs were discussed and proposed in a WHO manual²⁰ published in 2012 to help countries in their efforts to measure the impact of *Streptococcus pneumoniae* and *Haemophilus influenzae* type b conjugate vaccination in children. A prospective matched density case-control study design was proposed as standard. In this study design, cases are identified through the IPD surveillance system and controls are selected among the hospitalised (or outpatient/community) children free of disease at the moment of the case hospitalisation (matching by hospital, age and date of admission). The design was successfully used in the US for measuring PCV7 effectiveness using CDC's ABCs data²¹, and compared with the indirect cohort and screening methods.

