3.2 Secondary objectives

To measure the effectiveness of the PPSV23/PCV13:

- By age group among the elderly population, i.e. 65-74, 75–84 and ≥85 years
- By vaccine received: PCV13 or PPSV23 (if PCV13 recommended in the elderly population);
- Against specific vaccine serotypes, including vaccine related serotypes;
- Against different IPD clinical manifestations and SpCAP;
- Against different levels of IPD severity (ICU admission and/or length of hospital stay >14 days and/or presence of septic shock and/or intra-hospital death);
- Against antimicrobial non-susceptibility (by antibiotic tested);
- By time since vaccination.
- ► Each surveillance site to adapt the above objectives to the data sources available in the country/region.

4. Methods

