4.5.1 Case definitions

For the primary outcome, a case is a hospitalised person eligible for PPSV23 and/or PCV13 vaccination confirmed with an IPD according the ECDC case definition (below), in whom serotyping identified a vaccine serotype (PCV13 or PPSV23 IPD/SpCAP cases). The EC 2008 case definition should be used to recruit IPD cases²²:

PNEUMOCOCCAL INVASIVE DISEASE(S) (Streptococcus pneumoniae)

Clinical criteria

Not relevant for surveillance purposes

Laboratory criteria

At least one of the following three:

- Isolation of Streptococcus pneumoniae from a normally sterile site
- Detection of Streptococcus pneumoniae nucleic acid from a normally sterile site
- Detection of Streptococcus pneumoniae antigen from a normally sterile site

Epidemiological criteria

NA

Case classification

A. Possible case

NA

B. Probable case

NA

C. Confirmed case

Any person meeting the laboratory criteria

For secondary outcomes, the case is defined as above for the primary outcome, and in addition:

- A specific vaccine serotype is identified (this can be a vaccine serotype or vaccine related serotype);
- A clinical manifestation is identified as: meningitis, pneumonia, bacteraemia and others;
- Severity is assessed according to: ICU admission and/or length of hospital stay >14 days and/or death within 30 days.

²² European Commission, Commission Decision 2008/426/EC of 28 April 2008 amending Decision 2002/253/EC laying down case definitions for reporting communicable diseases to the Community network under Decision No 2119/98/EC of the European Parliament and of the Council (notified under document number C(2008) 1589)

► Each study site to state the case definitions for each primary and secondary outcome according to data collected.

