4.5.2 Reference group

The primary reference group comprises all persons ≥65 years eligible for vaccination, hospitalised for an IPD/SpCAP laboratory confirmed with a serotype identified as non-vaccine serotype (NVT, mainly nonPPSV23 controls) and excluding vaccine related serotypes. Cases with IPD/SpCAP due to vaccine related serotypes will be excluded from the analysis (i.e. serotypes from the same serogroups as the vaccine serotypes for which cross-protection was demonstrated or assumed).

For the secondary outcomes, the reference groups are the following:

- Specific vaccine serotype/ vaccine—related serotypes: NVT-IPD controls, same as for the primary outcome (see above);
- A [clinical manifestation]: NVT controls of the respective [clinical manifestation];
- Antimicrobial susceptibility: NVT controls in which antimicrobial susceptibility is investigated, and MIC provided (EUCAST thresholds will be taken into account for classification);
- Severe IPD cases: NVT-IPD controls admitted in the ICU / a length of hospital stay >14 days.

Matching

Matching can be an option when clustering by age, time or location is observed or the number of VT-IPD cases overpass NVT-IPD cases. For example, when the vaccine serotype IPD cases are clustered in certain age/location/time and NVT in other ages/locations/time, then matching/group matching by age/location/time would be required. Matching by region (or hospital if possible), age and time of hospitalisation (month/years) can be used²³.

► Each study site to describe the selection of the control group (all NVT controls) and matching by different variables (if it is the case) taking into account the outcome used.

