5.3 Measure of association

Vaccine effectiveness will be computed as 100% X (1 – the odds of vaccination in VT cases / odds of vaccination in NVT controls). An exact 95% confidence interval will be computed around the point estimate. The crude and adjusted estimates of vaccine effectiveness will be provided.

The VE will be computed for all exposures mentioned above.

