ageyears		Age of the case in years	Numeric	###	Age of patient in years as reported at the site level in years at time of hospital admission	

Variable name	Name of the variable in the site specific database	Variable label	Туре	Values and coding	Definition	Comments
sex		Gender	Code	0-female 1-male 9-unknown	Gender of the reported case	
dateadm		Date of the admission in the hospital	Date	dd/mm/yyyy	Date when the case was admitted to the hospital	
datedis		Date of the discharge from the hospital	Date	dd/mm/yyyy	Date when the case was discharged from the hospital	
outcome		Outcome	Code	0-alive 1-deceased 9-unknown	Information on survival at the end of hospitalisation: alive, deceased, unknown	
datedeath		Date of death	Date	dd/mm/yyyy	Date of death of the admitted patient (if outcome==1)	
clinic		Clinical entity	Multiple choice	0-unknown 1-meningitis 2-pneumonia 3- 4-bacteremia 5- 6- 9-other, specify	Clinical manifestation of the IPD case	This multiple-choice variable can be collected as such or each clinical entity can be entered separately using variables 12-20. If clinic =9, variable 20 (otherclin) specifies other

Variable name	Name of the variable in the site specific database	Variable label	Туре	Values and coding	Definition	Comments
						clinical entities of IPD not listed
meningitis		Pneumococcal meningitis	Code	0-no 1-yes 9-unknown	A case presenting with lab confirmed pneumococcal meningitis	
pneumonia		invasive pneumococcal pneumonia	Code	0-no 1-yes 9-unknown	A case presenting with lab confirmed pneumococcal pneumonia	
bacteremia		Bacteremia without known focus of infection		0-no 1-yes 9-unknown	A case presenting with lab confirmed bacteremia (blood stream infection) without known focus of infection	
otherclin		Other clinical entities	Text	String20	Other clinical entities of the IPD case	Please specify other clinical entity for the IPD cases
icuadm		Admission in the ICU	Code	0-no 1-yes 9-unknown	A lab confirmed case who needed admission in the ICU during the pneumococcal episode	
datediag		Date of diagnosis	Date	dd/mm/yyyy	Date when the diagnosis was made, should be the same with	

Variable name	Name of the variable in the site specific database	Variable label	Туре	Values and coding	Definition	Comments
					the identification/confirmation of the	
serotype		Serotype identified	Text	String3 PEN – pending NTP – non-typeable UKN - unknown	Serotype identified	

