These variables are included in the model to look at the interaction and define if there is effect modification. If effect modification is identified, then a stratified analysis will be conducted. The analysis can be done only if PCV and PPV are available by the effect modifiers strata:

Logit [PCV] = logit[PPV] + a +
$$b_xX_x$$
 +... b_kX_k

An adjusted VE and its 95% CI will be obtained.

► Each study site to describe additional studies used to validate the indirect cohort method.

-

²⁵ Idem 24

Version number	Date published	Text in original document	Changes included in the amended version	Comments
V2.1	15 Dec 2016	Page 14 (secondary outcomes) Page 14 (Case definitions for secondary outcomes) Table 3 "Clinical presentation (meningitis, pneumonia, sepsis)"	Modified by "Clinical presentation (meningitis, bacteraemic pneumonia, bacteraemia, other clinical presentations)"	Note that bacteraemia covers all bacteremia and not only bacteremia without focus (because in Denmark no difference between pneumonia and bacteremic pneumonia can be made) Decision during the technical meeting (Paris, September 2016) because the definition of sepsis is not homogenous over the sites.
		Page 15 (Case definitions for secondary outcomes and reference group) "Severity is assessed according to: ICU admission and/or length of hospital stay >14 days and/or presence of septic shock and/or intra-hospital death"	Modified as: "Severity is assessed according to: ICU admission and/or length of hospital stay >14 days and/or death within 30 days"	Decision during the technical meeting (Paris, September 2016
		Page 17: Definition of vaccination status	Included a definition for repeated vaccination	Decision during the technical meeting (Paris, September 2016)
		Page 17-18: confounders and effect modifiers Table 4: text replaced by the ICD codes for risk conditions	Modified to include the ICD codes for the underlying conditions	Decision during the technical meeting (Paris, September 2016)

		Table 4 ICD codes for IPD and SpCAP	Table 4 becomes table 2 and includes ICD codes for clinical IPD and SpCAP	Decision during the technical meeting (Paris, September 2016)
		Table 4: ICD codes for the underlying conditions by immune status	The new table 4 includes ICD 9 and 10 codes for underlying conditions	Decision during the technical meeting (Paris, September 2016)

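### Death within 30 days makes a vaccine-type patient a severe case but not a non-vaccine-type patient a severe control, so the secondary VE against severe IPD is open to selection bias of unknown direction and size

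*Protocol*

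**What the plan says.** Three places in the protocol define severe IPD, and no two agree.

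- **Section 4.5.1, for cases:** "Severity is assessed according to: ICU admission and/or length of hospital stay >14 days and/or death within 30 days".
- **Section 4.5.2, for controls:** "Severe IPD cases: NVT-IPD controls admitted in the ICU / a length of hospital stay >14 days". There is no death criterion.
- **Section 3.2, objectives:** "ICU admission and/or length of hospital stay >14 days and/or presence of septic shock and/or intra-hospital death". This adds septic shock and limits death to the hospital stay.

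Section 5.3 builds VE on "the odds of vaccination in VT cases / odds of vaccination in NVT controls", subtracted from one. Section 1.2 gives the condition that makes this meaningful: "the vaccination coverage among the IPD cases due to non-vaccine serotypes is similar to the vaccination coverage in the source population" that gives rise to the VT cases.

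In Table 3 the variable `outcome` is defined as "Information on survival at the end of hospitalisation: alive, deceased, unknown", and `datedeath` is completed only when that outcome is deceased.

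**The concern.** The indirect cohort design uses NVT patients to show the vaccine coverage of the population from which the VT cases come. When the outcome is narrowed to severe disease, the simplest way to keep that true is to narrow both groups by the same rule. Section 4.5.2 does so for clinical manifestations: controls must have the same manifestation as the cases. For severity it does not.

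The patients concerned die within 30 days, were never in an ICU and stayed 14 days or less. They count on the VT side only. Early death itself rules out a long stay, so without ICU care no other criterion brings the NVT patients among them back in. Section 4.7 lists age, underlying conditions and functional status as potential confounders, and early deaths outside the ICU plausibly differ from ICU and long-stay patients on all three. If their coverage differs as a result, the odds ratio for severe disease moves for a reason unrelated to the vaccine. Usable controls are lost as well.

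The three definitions also let sites diverge, although section 8 foresees a pooled EU/EEA analysis.

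**Working it through.** **1. The texts side by side** (the slash in 4.5.2 is read as *or*).

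| Criterion | 3.2 objective | 4.5.1 cases | 4.5.2 controls |
|---|---|---|---|
| ICU admission | yes | yes | yes |
| Stay over 14 days | yes | yes | yes |
| Death | in hospital | within 30 days | no |
| Septic shock | yes | no | no |

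The mismatch between 4.5.1 and 4.5.2 lies within the current text. The version table at the end of the protocol records the change to 30-day death as applying to the case definitions and the reference group. This is evidence only that one rule was intended for both; the point does not depend on it.

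**2. What the mismatch does to the estimator.** The protocol gives no VE, sample size or coverage figure specific to severe IPD, so there is no figure to reproduce. Every input below is an assumption, shown as a range:

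- *c*: coverage among NVT patients with ICU care or a long stay (0.3 or 0.5);
- *d*: share of all severe NVT patients, by the 4.5.1 rule, who qualify by death alone (10%, 20%, 30%);
- *g*: coverage in that share minus *c* (0, ±0.1, ±0.2);
- true VE 50%, the same in both kinds of severe patient, with the same ratio of VT to NVT disease among the unvaccinated in both.

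Coverage in controls under the full 4.5.1 rule is F = (1 − d)c + d(c + g) = c + dg. The odds of vaccination in VT cases are (1 − VE) × F/(1 − F). Section 4.5.2 divides these by c/(1 − c), so

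apparent VE = 1 − (1 − VE) × [F/(1 − F)] / [c/(1 − c)].

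Smallest non-zero shift, c = 0.5, d = 0.1, g = +0.1: F = 0.51, odds 1.041; apparent VE = 1 − 0.5 × 1.041/1 = 48.0%.

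Largest shift, c = 0.3, d = 0.3, g = +0.2: F = 0.36, odds 0.5625; apparent VE = 1 − 0.5 × 0.5625/0.4286 = 34.4%.

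Apparent VE (%) when the true VE is 50%:

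| c | d | g = −0.2 | −0.1 | 0 | +0.1 | +0.2 |
|---|---|---|---|---|---|---|
| 0.3 | 10% | 54.6 | 52.3 | 50.0 | 47.6 | 45.1 |
| 0.3 | 20% | 59.0 | 54.6 | 50.0 | 45.1 | 39.9 |
| 0.3 | 30% | 63.2 | 56.8 | 50.0 | 42.5 | 34.4 |
| 0.5 | 10% | 53.8 | 52.0 | 50.0 | 48.0 | 45.8 |
| 0.5 | 20% | 57.4 | 53.8 | 50.0 | 45.8 | 41.3 |
| 0.5 | 30% | 60.7 | 55.7 | 50.0 | 43.6 | 36.4 |

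Higher coverage among the death-only patients pulls VE down; lower coverage pushes it up. The error in points scales with 1 − VE. At a true VE of 70%, c = 0.5, d = 20% and g = ±0.1, the apparent VE is 67.5% or 72.3%.

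**3. The same rule on both sides.** The denominator becomes F/(1 − F), it cancels, and apparent VE equals true VE for every *c*, *d* and *g*.

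**The case against.** **The inconsistency need not cause bias.** With equal coverage (g = 0) the shift is zero at any *d*, and the protocol gives neither coverage by severity nor the share who qualify by death alone. This stands. A reader might infer that the severe-disease VE is biased; the text shows only that the two groups are selected differently.

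**Adjustment may remove it.** Sections 4.7, 5.4 and 5.5 plan collection of, stratification by and adjustment for age, underlying conditions and other factors, and Table 3 records institutional residence. The figures above are unadjusted, and adjustment could remove part of the shift. It would remove all of it only if the measured factors explained the whole coverage difference, which the plan gives no reason to rely on.

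**This is a generic protocol.** Sites state their own case definitions and describe how controls are chosen, so a careful site could align them. Nothing requires it to, and a site that follows the text builds the mismatch in.

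**Table 3 tempts to stronger claims.** One might infer that 30-day death cannot be ascertained, or that septic shock cannot be recorded. Neither is secure. Section 4.7 calls the table a minimum set, the table invites further site variables, and section 4.9 allows linkage of databases. Three codes of `clinic` have no legible label in the text at hand, and `otherclin` is free text. Deaths after discharge that `outcome` misses are missed among VT and NVT patients alike, so that gap is not the asymmetry at issue.

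**Conclusion.** The point holds as a contradiction between sections 4.5.1 and 4.5.2, with a third definition in 3.2 and no stated reason for the difference. It leaves the VE against severe IPD open to selection bias of unknown direction and size. Under the assumed inputs with a true VE of 50% and a non-zero coverage gap, the shift before adjustment runs from about 2 points to about 16 points down (34.4%) or 13 points up (63.2%). It is zero if coverage is equal.

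One of several secondary outcomes is affected. The primary VE does not use the severity rule, and a reader should not carry the concern over to it. This is a should-fix.

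**What to change.** 1. Add the death criterion of 4.5.1 to the severe reference group in 4.5.2, so that one rule selects VT cases and NVT controls.
2. Align objective 3.2 with that definition.
3. Reconcile Table 3 with the 30-day criterion: either extend `outcome` and `datedeath` to 30 days where linkage allows, or state that deaths after discharge are missed in both groups.

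Steps 1 and 2 are wording changes. They need no new patients and return to the analysis the NVT controls now left out. Step 3 costs nothing if the limitation is stated, and needs vital-status linkage at the sites if the definition is extended.

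### Severe IPD is defined differently for vaccine-type cases, for their non-vaccine-type controls and in the objective, leaving this secondary VE open to selection bias of unknown size and direction

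*Protocol*

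**What the plan says.** The protocol describes severe IPD in three places.

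- Section 3.2, the objective: "ICU admission and/or length of hospital stay >14 days and/or presence of septic shock and/or intra-hospital death".
- Section 4.5.1, the cases: "Severity is assessed according to: ICU admission and/or length of hospital stay >14 days and/or death within 30 days".
- Section 4.5.2, the reference group: "Severe IPD cases: NVT-IPD controls admitted in the ICU / a length of hospital stay >14 days".

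Elsewhere in its list, section 4.5.2 carries the case criterion over to the controls: "A [clinical manifestation]: NVT controls of the respective [clinical manifestation". Section 5.3 computes VE as one minus the ratio of "the odds of vaccination in VT cases / odds of vaccination in NVT controls". Section 1.2 gives the condition on which this rests: "The design is based on the assumption that the vaccination coverage among the IPD cases due to non-vaccine serotypes is similar" to the coverage in the population from which the VT cases arise. No section reconciles the three severity descriptions.

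**The concern.** A patient who dies early on a general ward, without ICU care and after a short stay, is a severe case if the serotype is vaccine-type. If the serotype is non-vaccine-type, the same patient is in neither group of the severe-disease analysis. Cases and controls then differ in the route by which they qualified as well as in serotype.

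In people aged 65 or over, those who qualify only by death may differ in age, frailty and underlying illness from those in ICU or with long stays. Section 4.7 lists age, functional status and underlying conditions as potential confounders, so equal vaccination coverage in the two kinds of patient cannot be taken for granted. Any difference in coverage passes straight into the odds ratio and would be read as lower or higher protection against severe disease.

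**Working it through.** **Comparing the texts**

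| Route to severe status | 3.2 objective | 4.5.1 cases | 4.5.2 controls |
|---|---|---|---|
| ICU admission | yes | yes | yes |
| Stay over 14 days | yes | yes | yes |
| Septic shock | yes | no | no |
| Death | in hospital | within 30 days | no |

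Only the first two routes are common to all three. Sections 4.5.1 and 4.5.2 differ on death alone. NVT patients who die after ICU admission or a stay over 14 days remain controls. Those lost are the deaths with neither.

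**Data on death.** Table 3 defines the outcome variable as survival at the end of hospitalisation and asks for a date of death only when that outcome is deceased. A death after discharge but within 30 days of onset or admission would not be captured by the listed variables.

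**Illustrative size.** The protocol gives no sample size or event count specific to severe IPD, so there is no figure of its own to reproduce. The inputs below are assumptions:

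- f: share of severe patients who qualify by death alone;
- pA: coverage in NVT patients with ICU admission or a long stay;
- pD: coverage in NVT patients who qualify by death alone;
- the same true VE in both kinds of patient, and the same f in VT and NVT disease.

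Coverage across all severe NVT patients is pm = (1 − f)·pA + f·pD. VT cases drawn from all three routes have odds of vaccination (1 − VE)·pm/(1 − pm). The controls in 4.5.2 have odds pA/(1 − pA). Hence

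expected OR = (1 − VE) × [pm/(1 − pm)] / [pA/(1 − pA)].

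Take true VE = 60%, pA = 50% (odds 1) and f = 20%:

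- pD = 70%: pm = 0.8 × 0.50 + 0.2 × 0.70 = 0.54; odds 0.54/0.46 = 1.174; OR = 0.4 × 1.174 = 0.470; VE = 53.0%.
- pD = 60%: pm = 0.52; odds 1.083; OR = 0.433; VE = 56.7%.
- pD = 50%: pm = 0.50; OR = 0.400; VE = 60.0%.
- pD = 40%: pm = 0.48; odds 0.923; OR = 0.369; VE = 63.1%.
- pD = 30%: pm = 0.46; odds 0.852; OR = 0.341; VE = 65.9%.

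Over the same ±20 points in pD, the range is 56.7% to 63.1% at f = 10% and 44.8% to 71.0% at f = 40%. For a true VE of 20% with pA = 50%, it is 6.1% to 31.9% at f = 20% and −10.5% to 42.1% at f = 40%.

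If controls meet the same definition as cases, both odds use pm, the ratio cancels, and OR = 1 − VE for any f, pA and pD.

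**The case against.** A reader might infer that VE against severe disease is biased, and biased downwards because patients dying on the ward are older and better vaccinated. The documents do not support that. They give neither the share of death-only patients nor coverage by severity. The bias vanishes if coverage is equal and reverses if it is lower. A reader might also infer that all NVT deaths are discarded, which goes too far for the reason given in the working.

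Three further points deserve weight.

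- **Adjustment.** Sections 4.5.2, 5.4 and 5.5 allow matching, stratification and multivariable logistic regression. To the extent that age and comorbidity drive the coverage difference, adjustment could remove part of it, and the figures above are unadjusted. This stands in part. Adjustment works only through measured covariates and leaves the definitions unequal. Table 3 shows no row for functional status, although sites may add variables.
- **Mirroring is not universal.** Section 4.5.2 compares serotype-specific cases with all NVT-IPD controls, and non-susceptible cases with NVT controls that were merely tested. An identical filter is therefore not the protocol's general rule. This also stands, but where controls are restricted by severity, a restriction that only partly matches the cases needs a reason, and none is given.
- **Site adaptation.** The protocol is generic, and sites must state their case definitions and describe how controls are selected. That gives each site a chance to correct the text, but nothing points them to the mismatch. Section 8 foresees a pooled EU/EEA article, for which sites resolving it differently would be a problem.

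The change log places the move to 30-day death under both case definitions and reference group. The gap between log and text is not itself the finding. The entry only suggests that one definition was intended and that this is an oversight.

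**Conclusion.** The point holds as an internal inconsistency affecting one secondary outcome. Followed as written, the current text applies different severity criteria to VT cases and NVT controls, and the objective uses a third set. Size and direction of any bias are unknown. Under the assumed inputs (true VE 60%, pA 50%, f 20%, no adjustment), a coverage difference of up to 20 points either way moves the expected VE by about 6 to 7 percentage points. A larger death-only share or a lower true VE makes the shift larger. The primary outcome and its reference group are not touched. It should be corrected, but it does not undermine the study as a whole.

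**What to change.** Use one severity definition, word for word, in sections 3.2, 4.5.1 and 4.5.2, and state that it applies identically to VT cases and NVT controls. Name the death window explicitly and choose one that the collected data support: either it matches survival at the end of hospitalisation, as in Table 3, or Table 3 is extended to capture later deaths. Where a site cannot ascertain a component, it should drop that component for VT and NVT patients alike and report this.

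The cost is a few lines of wording. Table 3 already lists ICU admission, admission and discharge dates, in-hospital outcome and date of death. Extra data are needed only if the chosen definition includes something not listed there, such as deaths after discharge.
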